Mothers who agreed to be contacted about the research visit will receive a call from a research assistant asking to schedule an in-home or virtual interview at a time when the child is typically awake and alert, when no or few other family members will be present, and when there will be an opportunity for the mother and research assistant to talk privately. The in-home research visit, which will take approximately 60 minutes, will be conducted by a 2-person team of research assistants. The use of 2-person teams will maximize the safety of the RA's in the community as well as the efficiency of the research protocol. Typically, RA #1 will focus on the mother while RA #2 handles assessment logistics including smooth presentation and removal of any assessment materials, and assistance with caring for the target child and any other children in the home. For in-home interviews, the following procedures will be conducted: (a) informed consent procedures (described in detail under Recruitment, below); (b) the psychosocial interview. Upon completion of these procedures, mothers will be paid \$50 cash and will receive a list of mental health resources.

The virtual interviews, which will take approximately 60 minutes, will be conducted by one research assistant through a video conferencing platform (Zoom, FaceTime, Skype, or Webex) or by phone. The following procedures will be conducted: (a) verbal informed consent procedures (described in detail under Informed Consent below); (b) the psychosocial interview. One of two payment options will then be provided: cash or electronic gift card. For cash incentives, within one week of the virtual interview, a team of 2 RA's will hand deliver \$50 cash and list of mental health resources to the participant's home. The second option, electronic gift cards, will be sent to mothers via email along with the list of mental health resources.

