The psychosocial interview will assess the domains of infant health care, maternal wellbeing, maternal adverse childhood experiences, maternal adult attachment security, use of community services, including child care, neighborhood collective efficacy (community support), and quality of the home environment, including home safety and supportive parenting by both mothers and fathers (including non-resident fathers). Basic demographic questions will also be asked. Wherever possible, we will use standardized and widely used research assessments (e.g., the Edinburgh Postpartum Depression Scale, the 10-item Adverse Childhood Experiences (ACEs) questionnaire, the Home Observation Measurement of the Environment [HOME] assessment). The principal research assistant (typically RA #1) will administer all assessments via structured interview, with responses recorded on a secure electronic tablet. RA #1 will complete the following steps before administering the ACEs questionnaire: 1. Briefly explain what ACEs are and why they are important to understand; 2. Remind participants that their scores are private, but if we learn that an experience of childhood maltreatment was not reported, we will be legally obligated to consult appropriate authorities about the possibility of making a report; 3. Remind participants that they can stop at any point, refuse to respond, or talk about how they are feeling; 4. Remind participants that we are providing all participants with a list of mental health resources, including the phone number for a 24-hour parent hotline staffed by [REDACTED]. In addition, per HOME protocol, the principal research assistant will observe, rate, and record several qualities of the home environment and the mother's parenting behaviors.

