Research staff will monitor participants and minimize risks. These risks include (a) increased maternal sadness or worry evoked by questions about adverse childhood experiences, and (b) breach of confidentiality. In case mothers disclose risk of self-harm, child maltreatment, or screen positive for postpartum depressive symptoms, a list of mental health resources will be provided to all participants. This list will include resources from The [REDACTED] and other appropriate community referrals. Efforts to monitor and minimize risks will be conducted at every stage of the research process and are detailed below. Breach of confidentiality will be minimized by procedures for handling data that will safeguard confidentiality. When texting reminders before the 6-month psychosocial interview, full names and confidential identification numbers will not be used or linked. Research staff will copy/paste the monthly text message from the Notes app or manually type in each message. Moreover, all project cell phones will be password protected, and these cell phones will be used only by the study team members. Participant names will not be used on any data collection forms. Participants will be assigned confidential ID numbers. There will be a master list linking participants' IDs and personal contact information (names, addresses, and phone numbers). This list as well as the signed project consent forms will be kept in locked cabinets secured within the project office. Only investigators and staff members who are directly involved in the data collection and processing will have access to the master list or portions thereof. During the home visit, all precautions will be taken to ensure that the interview is conducted in privacy.

With maternal permission (requested on the consent form), the following records for the target child will be accessed and analyzed: (a) records from Sinai Hospital and/or the Maryland Department of Health; (b) records from the Maryland Department of Human Services; (c) records from the Maryland Family Connects program; and (d) records from the Maryland State Department of Education, all of which will be reviewed for child health and family service needs and receipt until the target child is 6 years of age.

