5.1 If Yes, what procedures are in place to assure safety?

We are explicit in the consent and assent forms that we are mandated reporters. If we learn that keeping specific information private would put the participant or others in danger, we may discuss it with them, if possible, or voluntarily seek help from appropriate authorities to protect the participant or the other person. This includes if there is a risk of the participant hurting themselves. If we learn of any risks to the child's safety (for example, child abuse or neglect) or unreported childhood maltreatment, we inform the participant that we will report any concerns to the authorities. We will have a list of mental health resources to provide to all participants.

ID: VIEW4E09460F5EC00

Name: v2\_Surveys/Questionnaires

View: v2\_Clinical Trial Registration

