**1.1 If Other, specify:**

2 \* What is the total dollar value of the payments/reimbursements over the duration of the study? **Total payment(s) for participation in research of \$600 or more is required to be reported on an IRS Form 1099.**  
50.00

3 \* Describe the timing and distribution plan for the payment/reimbursement (schedule, means, etc.)?

Participant will be given a one-time payment of \$50.00 cash in person or \$50 electronic gift card, at the completion of the 6-month research assessment. For in-home interviews, the cash payment will be given at the conclusion of the interview. For virtual interviews, the cash payment or electronic gift card payment will be given to participants within one week of their completed interview.

4 \* Method(s) of payment/reimbursement to be Used:

- Cash
- Check
- Money Order
- Gift Certificate/Gift Card
- Other

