## Informed Consent Process

**If the study does not involve interaction with participants or a waiver of consent is being requested , answer "N/A" to the questions below.**

1 \* Indicate the type(s) of consent that will be involved in this study: (check all that apply)

- Not applicable (study may qualify as exempt)
- Request to Waive Consent/Parental Permission (Consent is not being obtained)
- Request to Alter Consent (Some Elements of Consent Waived)
- Request to Waive Documentation of Consent (Verbal/Oral Consent)
- Written Consent Form
- Electronic Consent

2 \* Describe the Informed Consent process in detail:

From July 15, 2019 - January 14, 2021, research staff will approach all of these new mothers within 1-3 days of the birth of the baby. The researchers will provide mothers with a brief description of the study and a 1-page information sheet (see attached). The study will be explained to the mothers as a "study of what it is like to raise a baby in Baltimore City." The researchers will request verbal permission to contact the mothers when their infants are approximately 6 months old to schedule the in-home or virtual interview assessment. Informed consent will be collected at the time of this assessment. For virtual interviews, the consent form will be read to participants word-for-word and participants will consent verbally. During the initial contact, the researchers will also confirm mothers' contact information and share their own contact information. Last, all mothers who agree to be contacted will also receive monthly postcards providing a "fun fact" about typical infant developmental milestones.

3 Confirm that the consent process will explain the following:

- The activities involve research.
- The procedures to be performed.
- That participation is voluntary.
- The name and contact information for the investigator.

\*  Yes  No

4 \* Describe who will obtain Informed Consent:

Research staff from the University of Maryland will obtain the Informed Consent document (or verbal consent) from participants.

5 \* If obtaining consent from a legally authorized representative (LAR), describe how you will confirm that the individual is the LAR and can provide legally effective informed consent. (Answer "N/A" if not obtaining consent from LARs)

N/A

6 \* Describe the setting for consent:

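### After a virtual interview, the written mental health resource list travels with the payment and may arrive up to one week later; in-home mothers receive it when the interview ends

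*Protocol*

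**What the plan says.** Study Procedures, item 1, describes two modes for the 6-month interview.

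- **In-home.** When consent and interview are complete, the mother is paid "and will receive a list of mental health resources".
- **Virtual, cash.** "For cash incentives, within one week of the virtual interview, a team of 2 RA's will hand deliver" the cash together with the list.
- **Virtual, gift card.** "The second option, electronic gift cards, will be sent to mothers via email along with the list of mental health resources". No timing is given at this place. Payment/Reimbursement Detail, item 3, supplies the limit: "For virtual interviews, the cash payment or electronic gift card payment will be given to participants within one week of their completed interview".

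The same section gives the list its safety role: "In case mothers disclose risk of self-harm, child maltreatment, or screen positive for postpartum depressive symptoms, a list of mental health resources will be provided", and it goes to all participants. Resources, item 3, and Potential Benefits and Alternatives, item 3, describe the list in the same role.

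Before the adverse childhood experiences (ACEs) questions, one of the research assistant's steps is: "Remind participants that we are providing all participants with a list of mental health resources, including the phone number for a 24-hour parent hotline". Waiver of Documentation of Consent, item 2, states that 6-month interviews were not being held in person at that time.

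**The concern.** In virtual mode a safety item follows a payment schedule. A one-week limit is reasonable for delivering cash. The list has a different purpose: it supports a mother who has just been screened for depression and asked about her own childhood adversity. Research Related Risks, item 1, rates some sadness or worry from such questions as somewhat likely and names the list among the provisions against it.

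At stake is participant protection. A mother who screens positive on the Edinburgh scale by phone or video, or who is distressed by the ACEs items, may hold no written list for some days. An in-home mother with the same answers has it when the interview ends. The in-home arrangement shows what the study itself regards as workable, and virtual was the mode in use when this version was written.

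**Working it through.** The plan gives no figure to reproduce. The check compares the timing rules and then asks whether any other provision closes the gap.

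**Step 1. Permitted wait from the end of the interview to the written list.**

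| Mode | Rule and source | Permitted wait |
|---|---|---|
| In-home | On completion (Study Procedures, item 1) | 0 days |
| Virtual, cash | Hand delivered with the cash within one week (Study Procedures, item 1) | 0 to 7 days |
| Virtual, gift card | Emailed with the card (Study Procedures, item 1); card due within one week (Payment/Reimbursement Detail, item 3) | 0 to 7 days |

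The largest permitted difference between modes is 7 − 0 = 7 days. This is a maximum. For the gift card it comes from combining two sections, and an email sent straight after the call would comply.

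**Step 2. Does anything require earlier delivery?** No visible section tells staff to send the list before, during or at the end of a virtual interview.

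**Step 3. What do the other safeguards cover?**

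- *Oral reminder.* Before the ACEs items the mother is told about the list and its hotline, and that she may stop, decline to answer or talk about how she feels (Study Procedures, item 1). Reading the number aloud is not specified.
- *Replies to texts.* If a mother's text discloses something concerning, such as depressive symptoms, staff provide resource information (Study Procedures, item 1; Recruitment, item 1). This depends on her writing and, in context, mainly concerns the months before the interview.
- *Danger.* Where keeping information private would endanger someone, including through self-harm, staff may discuss it with her or "voluntarily seek help from appropriate authorities to protect the participant or the other person" (Surveys/Questionnaires, item 5.1).
- *Serious risk of harm.* The research assistant involves the supervisor or principal investigator when a protective services report is warranted (Research Related Risks, item 1).

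The last two respond to danger or serious harm. A positive depression screen without such danger is met, in the visible text, only by the list. None of the four brings the written list forward.

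**Step 4. How many mothers?** The number of virtual interviews is not stated. It is above 0 if interviews took place while in-person meetings were suspended (Waiver of Documentation of Consent, item 2). It is at most 400, the planned enrolment (Participant Selection, item 2). The documents give no basis for a narrower range and no rate of positive screens or distress.

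**The case against.** The strongest reply is that only the arrival of a written sheet is shown to be late, and that a virtual mother may already have what matters most. The reminder before the ACEs items mentions the hotline number and can be read as giving it. In addition, "For virtual interviews, the consent form will be read to participants word-for-word and participants will consent verbally", and that form may contain the number. Neither the consent text nor the interview instrument is visible here. This stands. A reader might infer that a virtual mother is left without a hotline number or any support for a week; the documents do not support that, because the unseen texts may supply the number and the other safeguards apply in both modes.

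A second reply is that one week is a limit and not a practice, especially for an emailed card. This also stands, so seven days should not be read as the expected delay. If same-day sending is already the practice, writing it down costs almost nothing.

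A third reply is that the point has no statistical consequence and may come too late. The first part is correct: nothing ties interview mode to study group, the list follows the interview in both modes, and its timing enters no model in the SAP. A reader who inferred bias in the group comparison would go beyond the documents. On timing, recruitment was planned to end on January 14, 2021, which puts the last 6-month interviews at about mid-July 2021, while the SAP was last updated on July 18, 2023. If no virtual interviews remain, the change cannot help this trial.

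**Conclusion.** The point holds as a minor participant-protection improvement in a study described as minimal risk. For virtual interviews the written list may arrive 0 to 7 days after the interview, against 0 days in-home, and the list is the only response visibly named for a positive depression screen. It is a difference between two modes and not a contradiction: each rule is clear, and every participant is meant to receive the list.

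This rests on the visible text being complete on when the list is delivered. It does not rest on any claim about the hotline number, which cannot be settled here. The number of mothers affected lies above 0 and at or below 400, and the point applies only to virtual interviews still to be done under this version.

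**What to change.** Amend Study Procedures, item 1, so that every virtual participant is sent the list, including the 24-hour hotline number, at the end of the interview, by email or text as she prefers. Separate this from the payment, which keeps its one-week limit.

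- **At the end, not before.** In-home mothers receive the list after answering the questions. Sending it earlier in virtual mode would create a new difference between modes.
- **To everyone, whatever the answers.** This keeps the existing all-participants rule and does not reveal a screening result.
- **With the existing texting precautions** in Study Procedures, item 1: no full names and no ID numbers. Texting is described there for reminders and replies, and email for the gift card option, so the new use of both channels should be written into the modification.

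The cost is a short modification to the IRB (required for changes after approval, Final Page of Application) and one message per virtual participant, at most 400. No extra staff or visit is needed. The downside is a small privacy risk if mental health material reaches a shared phone, which letting the mother choose the channel reduces. What clinical response a disclosure should trigger remains for the investigators and the IRB.

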## Sample Size and Data Analysis

**If you uploaded a separate research protocol document in the 'Research Protocol' page, cite the applicable section and page numbers from that document in the answer boxes below.**

1 \* Provide the rationale and sample size calculations for the proposed target population:  
Following guidelines established by Cohen (1988) and using Gpower software (Faul et al., 2009), power analyses estimating at least 0.80 power and a significance level of 0.05 indicated that a sample size of 400 (assuming equal groups) will detect small to medium effects in most of the outcomes of interest. Some outcomes are more exploratory in nature. In addition, it is possible that additional research funding garnered in the course of this study will allow for an increased sample size.

2 \* Provide the plan for data analysis. Include in the description the types of comparisons that are planned (e.g., comparison of means, comparison of proportions, regressions, analysis of variance, etc.), which is the primary comparison/analysis, and how the analyses proposed will relate to the primary purposes of the study:  
The principal independent variable will be MFC group (MFC participant/non-participant). The dependent variables of interest will be (a) infant emergency room use and overnight hospital stays; (b) family use of community resources and child care; (c) maternal wellbeing; and (d) quality of the home environment. We will also explore long-term differences between MFC and non-MFC participants in (a) rates of official investigations for child maltreatment and (b) two indicators of early educational achievement: kindergarten readiness scores and rates of kindergarten attendance.

A two-tailed intent-to-treat design analysis will include all randomly assigned families (regardless of actual intervention participation). Ordinary least squares regression models will be used to estimate impact of MFC on continuous and categorical outcomes. Poisson regression models will be used for count variables with skewed distribution. Covariates for all models will include the following: Medicaid status (yes/no) at birth and at 6 months, mother race/ethnicity (nonminority/minority), single parent household (yes/no), birth complications (yes/no) including maternal health conditions affecting the baby, infant injuries from birth trauma, and infant distress. Exploratory moderators will include infant birthweight, family Medicaid status, and mothers' adverse childhood experiences and adult attachment security. All results will be analyzed at the .05 significance level.

ID: VIEW4E02806052800  
Name: v2\_Sample Size and Data Analysis

View: v2\_Sharing of Results

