Hospital, both located in Baltimore, MD. For the purposes of this study, Sinai Hospital will serve as the community/catchment area. Nurse home visitors recruit these new mothers while they are still in the hospital/maternity ward. Following Dodge et al. (2013; 2014), when the [REDACTED] officially begins, nurse home visitors will enroll new mothers into MFC every other day only (on odd dates). Those new mothers who are not City residents and/or give birth on an even date will not be offered MFC. They will be considered the "control" group and are expected to access community services as they normally would. [REDACTED] staff will recruit ALL Baltimore City residents who give birth at Sinai Hospital, regardless of odd/even birth date, while they are still in the hospital/maternity ward and with post-discharge outreach. If a mother who gives birth on an odd date declines the MFC program, she will still be recruited into the research study. Given that the effects of MFC are a key study question, and MFC is being provided on a random-assignment basis according to child birthdate, this study follows a RCT design. At the same time, we note that its approach is different than many RCT's, in that prospective research participants are not being explicitly invited to be randomized.

3 \* **Describe the relevant prior experience and gaps in current knowledge. Describe any relevant preliminary data:**  
 While nurse home visiting programs have been shown to be effective in reducing infant injuries and improving outcomes for children and families, Family Connects is the first nurse home visiting program to be implemented on a community-wide scale. Evaluations of the Family Connects Program has been conducted by Dodge and colleagues in Durham, North Carolina (Dodge et al., 2013; 2014), demonstrating positive effects such as reduced infant emergency room use and overnight hospital stays, increased families' use of community resources, and improved family well-being. No randomized controlled trials of Family Connects have occurred outside of North Carolina, however. The proposed study seeks to expand the research on the Family Connects Program and assess its outcomes in a mid-sized, mid-Atlantic city.

4 \* **Provide the scientific or scholarly background, rationale, and significance of the research and how it will add to existing knowledge:**  

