## Surveys/Questionnaires

You indicated that this study involves surveys and/or questionnaires.

If you uploaded a separate research protocol document in the 'Research Protocol' page, cite the applicable section and page numbers from that document in the answer boxes below.

- 1 \* List all questionnaires/surveys to be used in the study, including both standardized and non-standardized assessments:  
The psychosocial interview will assess the domains of infant health care, maternal wellbeing, maternal adverse childhood experiences, maternal adult attachment security, use of community services, including child care, neighborhood collective efficacy (community support), and quality of the home environment, including home safety and supportive parenting by both mothers and fathers (including non-resident fathers). Basic demographic questions will also be asked. Wherever possible, we will use standardized and widely used research assessments (e.g., the Edinburgh Postpartum Depression Scale, the 10-item Adverse Childhood Experiences (ACEs) questionnaire, the Home Observation Measurement of the Environment [HOME] assessment).
- 2 \* Upload a copy of all questionnaires/surveys:  

Name	Created	Modified Date
BBP 6-month Psychosocial Interview	2/7/2019 2:37 PM	1/24/2020 2:39 PM
- 3 \* What is the total length of time that each survey is expected to take?  
We have one psychosocial survey that we expect will take 60 minutes to complete.
- 4 \* Are any of the questions likely to cause discomfort in participants or cause harm if their confidentiality were breached? (i.e., Illegal activities)  
 Yes  No
- 5 \* Do any questions elicit information related to the potential for harm to self or others?  
 Yes  No

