The researchers will request permission to contact the mothers when their infants are approximately 6 months old to schedule the in-home or virtual interview assessment. Informed consent will be collected at the time of this assessment. During recruitment, the researchers will also confirm mothers' home address and phone number and share their own contact information. Last, all mothers who agree to be contacted will also receive monthly postcards and text messages providing a "fun fact" about typical infant developmental milestones and monthly text messages to remind them that we will be inviting them to participate in the psychosocial interview around the time of their infant's 6-month birthday. Research staff will copy/paste the monthly text message from the Notes app or manually type in each message. If a mother texts the RA's work cell phone with questions about the study, the RA will respond with the appropriate information (e.g., interview location). In cases where a mother may disclose concerning information (e.g., depressive symptoms), information about mental health resources will be provided. This list will include resources from The [REDACTED] and other appropriate community referrals.

[REDACTED] will not be recruiting from the University of Maryland Baltimore.

We note that without the hospital's ongoing provision of information about their maternity patients, the research could not be practically carried out because we would not be able to identify prospective participants. The hospital has agreed to share this information with the study team.

The [REDACTED] nurse home visitors will be providing information about MFC to eligible mothers upon program recruitment and enrollment whereas the [REDACTED] will be presented as a study of what it's like to raise a baby in Baltimore. Research staff will not discuss MFC directly, as only approximately half of the research participants will have been recruited into MFC. Research staff do not plan to debrief research participants on the impacts of MFC.

**2 \* Describe measures that will be implemented to avoid participant coercion or undue influence (if not applicable to the study, enter "N/A"):**

Research staff will explain to potential participants that participation in the study is completely voluntary and that they may opt out at any time. Participation in the study will not be linked to the services they receive from Sinai Hospital or from any other institution or agency.

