## Children (Assent)

You indicated that children are included in this study.

1 \* From whom will assent be obtained?

- All children
- None of the children
- Some children

1.1 If assent will be obtained from some children, describe which children will not be asked for assent and why:

2 \* How will assent be documented? (Answer "N/A" if assent will not be obtained from any of the children)

For those mothers under 18 years old, they will sign (or verbally agree to) a separate assent form, and their parent/guardian will additionally sign (or verbally agree to) a consent form. All participants will also be signing (or verbally agreeing to) their consent/assent to access their child's records.

ID: VIEW4E1B2E37C1C00  
Name: v2\_Children (Assent)

View: v2\_Consent Forms - Draft

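### The covariate list for all models leaves out maternal age at delivery; adding it is a small, nearly free improvement, not the correction of an error

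*Protocol*

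**What the plan says.** Protocol, Sample Size and Data Analysis, item 2, and the second paragraph of the SAP give the same list: "Covariates for all models will include the following: Medicaid status (yes/no) at birth and at 6 months, mother race/ethnicity (nonminority/minority), single parent household (yes/no"), followed by "birth complications (yes/no) including maternal health conditions affecting the baby, infant injuries from birth trauma, and infant distress". The list applies to every model. Maternal age is not a moderator either: "Exploratory moderators will include infant birthweight, family Medicaid status, and mothers' adverse childhood experiences and adult attachment security". Neither document explains how the covariates were chosen.

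The other relevant statements are all in the protocol:

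- **Age and consent.** Children (Assent), item 2: "For those mothers under 18 years old, they will sign (or verbally agree to) a separate assent form". A parent or guardian must also consent for these mothers.
- **Possible sources of age.** Surveys/Questionnaires, item 1: "Basic demographic questions will also be asked". The Lay Summary says that permission will be sought for the child's official birth record. The list of records in Study Procedures, item 1, does not include it.
- **Assignment.** Justification, Objective, & Research Design, item 2: "MFC is being provided on a random-assignment basis according to child birthdate". No balancing on age is described.
- **Timing of consent.** Recruitment, item 1: "Informed consent will be collected at the time of this assessment". The assessment referred to is the interview at about 6 months.
- **Sample size.** Sample Size and Data Analysis, item 1: "power analyses estimating at least 0.80 power and a significance level of 0.05 indicated that a sample size of 400 (assuming equal groups"). The target effect is described only as small to medium. No standardised difference, SD or event rate is given.

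**The concern.** A useful adjustment variable is fixed before assignment, plausibly prognostic and cheap to obtain. Age at delivery meets the first condition without argument. The protocol makes the third very likely. The second is a reasonable expectation for outcomes such as maternal wellbeing and infant emergency care, but the documents do not establish it.

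Two things are at stake. One is precision: a prognostic covariate left out stays in the residual variance. The other is comparability. Interview outcomes exist only for mothers who consent at about 6 months, after the nurse home visits that Supporting Literature, item 1, places at 3 to 8 weeks. Participant Selection anticipates 700 screened and 400 enrolled. An age difference between the consenting groups therefore need not be pure chance, and with age outside the model, the part of it that the listed covariates do not capture would stay in the MFC coefficient.

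**Working it through.** **Inputs from the protocol:** N = 400, equal groups (200 per arm), two-sided 0.05, power 0.80. **Assumed:** R², the share of outcome variance that age explains beyond the listed covariates. Both d and R² are expressed relative to the variance left after those covariates. The documents give no value, so a range is shown.

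**Step 1. The plan's own figure.** No numeric effect size is stated, so 400 can only be inverted. The standard error of a difference in means, in SD units, is √(2/200) = 0.1. The detectable difference is (1.960 + 0.842) × 0.1 = 0.280. In the other direction, d = 0.28 needs 402 in total, d = 0.20 needs 786 and d = 0.50 needs 126. So 400 fits a small-to-medium effect of about 0.28. That value is back-solved, not an independent reproduction.

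**Step 2. Precision gained by adding age (continuous outcome, least squares).** The residual SD is multiplied by √(1 − R²), which gives:

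- detectable d = 0.280 × √(1 − R²)
- power at d = 0.28 is Φ(0.28 / (0.1 × √(1 − R²)) − 1.960)
- equivalent extra families = 400/(1 − R²) − 400

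| Assumed R² | Detectable d | Power at d = 0.28 | Equivalent extra families |
|---|---|---|---|
| 0 | 0.280 | 0.800 | 0 |
| 0.01 | 0.279 | 0.803 | 4 |
| 0.02 | 0.277 | 0.807 | 8 |
| 0.05 | 0.273 | 0.819 | 21 |
| 0.10 | 0.266 | 0.839 | 44 |

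**Step 3. Effect of an age imbalance if age stays out of the model.** The shift in the MFC estimate is b = (residual imbalance in SD) × √R². Under random assignment at 200 per arm, the 95% chance limit for the imbalance is 1.96 × 0.1 = 0.196 SD. For R² = 0.01, 0.02, 0.05 and 0.10, b = 0.020, 0.028, 0.044 and 0.062 SD.

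Given that imbalance, the rejection rate under no effect is 1 − Φ((0.196 − b)/s) + Φ((−0.196 − b)/s), with s = 0.1 × √(1 − R²). This gives 5.3%, 5.6%, 6.6% and 8.2%. These rates are conditional on an imbalance at the edge of chance. Averaged over valid randomisation, the rate is 5% with or without age.

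**Step 4. Is age available?** The assent rule requires staff to establish whether each consenting mother is under 18. It does not show that exact age is recorded. Basic demographics and the birth record would normally hold it, but the text does not name age or maternal date of birth as a field. Availability is very likely, not shown.

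No calculation was made for the Poisson models planned for skewed counts, which may include emergency room use and overnight stays.

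**The case against.** The strongest reply is that nothing here is wrong. The two documents agree on a single pre-specified list. Leaving one baseline variable out of a randomised intent-to-treat comparison causes no bias on average, and education or parity could be proposed on the same grounds. All of this stands. It limits the point to a suggested improvement whose value is unknown until the prognostic strength of age is known. Parsimony is a weaker defence: one term costs one degree of freedom, and the list already contains a variable measured after MFC contact, Medicaid status at 6 months.

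A reader might infer two stronger claims. The documents support neither.

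- **That the guardian requirement makes the age mix differ by arm.** The rule is the same in both arms, and a common filter does not create an arm difference. That would need consent to depend on arm and age jointly, which nothing in the protocol shows. All mothers are to be approached within 1 to 3 days of birth, and research staff are not to discuss MFC. Late consent leaves differential selection possible, but that is a broader issue, and adjusting for age addresses only its age part. A linear term addresses only a linear age effect.
- **That the true error rate is well above 5%.** Take a 0.2 or 0.3 SD imbalance and an age-outcome correlation of 0.2. The shift is 0.04 or 0.06 SD, and the rejection rate is 1 − Φ(1.96 − 0.4) + Φ(−1.96 − 0.4) = 6.9%, or 9.2% with 0.6 in place of 0.4. The arithmetic is correct, but the imbalances are about 2 and 3 chance standard errors. The sum also uses the raw correlation and imbalance, where what matters is what remains after the listed covariates. These are conditional illustrations, not the trial's error rate.

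**Conclusion.** The omission is real and identical in both documents. It is a minor missed opportunity, not an error or an inconsistency. For a continuous outcome, if age explains a further 1% to 5% of the variance, adding it raises power at d = 0.28 by 0.4 to 1.9 percentage points (about 0.800 to between 0.803 and 0.819), worth about 4 to 21 families out of 400. A gain of more than 2 points needs age to explain slightly more than 5%.

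Some protection against residual age imbalance among consenting families comes with it, in part only. The documents do not support reading the omission as a source of bias or of an inflated overall error rate. The conclusion rests on the assumed R² range, on linear models for continuous outcomes, and on exact age being held.

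**What to change.** 1. Confirm that the mother's exact age, or her date of birth, is recorded in the interview or the birth record.
2. If it is, add mother's age at delivery (years, continuous) to the covariates for all models in Protocol, Sample Size and Data Analysis, item 2, and in the SAP. If it is not, or if the sponsor prefers to leave age out, state the reason.
3. For outcomes already analysed, keep the listed model and report the age-adjusted result as a labelled sensitivity analysis.
4. Tabulate maternal age by assigned arm among consenting families, to show whether there is an imbalance to adjust for.

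The cost is one phrase in each document and one degree of freedom out of about 400. No new data collection is needed if step 1 is confirmed.
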